Exercise as a buffer against stress induced overeating
ClinicalTrials.gov #: NCT02936076

Study Protocol
10.11.17

Study overview: Subjects will be recruited to participate in this study via advertisements in local newspapers, internet postings, and community newsletters. Interested individuals will be screened via the telephone to determine initial eligibility (see full eligibility criteria below). If deemed eligible via the phone screen, participants will be invited to an orientation session where they will learn additional details about the study, sign an informed consent document, and complete baseline assessment measures. Participants will then be randomized to a 12-week exercise training program or a delayed exercise condition (see below for more details). Assessments will take place at baseline and 12 weeks. Participants will not be compensated for the baseline assessment visit. At 12 weeks, they will be compensated \$25 for completing study questionnaires, a food choice computer task, and measures of weight, fitness and body composition. Further, at baseline and 12 weeks, participants will be asked to respond to prompts via their smartphone 5x/day over a 14-day period while also wearing an armband that objectively measures physical activity. At week 12, participants will receive \$0.50 for each EMA prompt responded to within 45 minutes and a completer's bonus of \$30 if they have >80% compliance and wore the armband for at least 9 days for ≥ 10 hours/day.

Eligibility criteria: To be eligible for the study, participants must be female, aged 18-60, have a BMI of 25 to 40 kg/m^2 , own a smartphone, and be willing to receive and respond to text message prompts for 14 days at baseline and 12 weeks. Exclusionary criteria include: shift workers, those who do not endorse stress-eating, recent weight loss or current enrollment in a weight loss program, women who are pregnant, those with any medical condition that would limit participation in physical activity, diabetes, or an inability to walk without an assisted device or inability to meet exercise recommendations. Participants with a previous history of heart disease or hypertension will be required to provide physician consent prior to participating in this study. Further, individuals with <80% compliance to the EMA monitoring at baseline or those with poor compliance to wearing the armband will not be eligible to participate.

Treatment conditions:

- Exercise condition:** Participants randomized to the exercise condition will participate in a 12-week exercise training program and asked not to alter their dietary habits during this time. The exercise intervention will consist of both supervised and unsupervised exercise sessions. The exercise prescription will start out at 100 minutes/week of moderate-intensity exercise and progress to 200 minutes/week. During the first 4 weeks, they will engage in 2 supervised exercise visits/week in which their heart rate will be monitored by a member of the research staff to ensure that exercise is within the prescribed intensity range. During Weeks 5-12, participants will engage in 1 supervised visit/week. At these supervised exercise visits, heart rate, ratings of perceived exertion and feeling state will be assessed periodically. The remaining exercise will be performed on their own. To help facilitate exercise adherence, participants will be required to have a gym membership and will be reimbursed up to \$40/month depending upon the cost of their local gym. Further, 'exercise' participants will be given an armband to wear over the 12-week period during all exercise sessions in order to verify compliance to the exercise protocol. Since the goal of this study is to determine how exercise training influences eating behaviors and other psychological parameters, participants will be incentivized to exercise. They will receive \$10 in cash for each week that they meet the exercise goal and a \$50 bonus (in the form of a gift card) if they averaged >180 min/week over the 12-week period as verified via the armband. Thus, they can receive a total of \$170 for performing the prescribed exercise.
- Delayed exercise condition:** Participants randomized to the delayed exercise condition will be asked not to change their exercise or eating habits over the 12-week period and will complete the same assessment measures as the exercise condition. However, following the completion of the 12-week assessment period, participants will be given two options: 1) receive a one-on-one session with an exercise physiologist at our center and receive a written exercise program, or 2) complete the identical exercise protocol as the 'exercise' condition. If participants choose option 2, they will receive the exact program outlined above and also complete additional assessments at 24 weeks (similar to those described for week 12).

Assessment measures:

In-person visit: Height will be assessed at baseline and weight and body composition will be assessed at baseline and 12 weeks. Body composition will be assessed via bioelectrical impedance analysis (RJL Systems Quantum II impedance machine). Participants will be asked to fast for 4 hours, refrain from alcohol for at least 12 hours, and to refrain from strenuous exercise or sauna for 8 hours prior to these measures. As part of these assessment visits, participants will also be given a series of questionnaires (see measures below), be equipped with an armband (used to measure physical activity), and will be instructed on how to respond to the EMA prompts over the 14-day EMA period.

EMA protocol: Participants will be asked to carry their smartphone for 14 days at baseline and 14 days at the end of the intervention. They will report on their stress, mood, hunger, physical activity, overeating episodes, and dietary temptations/lapses as they occur in their natural environment. All entries will be made in response to 5 semi-random prompts delivered throughout the day (between 8:00am and 10:00pm) via text message. Upon receiving the text message, participants will have 45 minutes to click on the link provided and this will direct them to an online questionnaire. Each set of questions will take 3-5 minutes to complete and individuals <80% compliant at baseline will be ineligible to participate in the study.

Sensewear Armband: Participants will wear a Sensewear armband (Body Media, Pittsburgh, PA) for 14 consecutive days (to coincide with the EMA monitoring period) at baseline and 12 weeks. This device is worn on the upper arm and provides valid and reliable estimates of exercise intensity and energy expenditure via a unique combination of sensors (accelerometer, galvanic skin response, heat flux, and skin temperature). Structured exercise bouts (≥ 10 minutes of activity ≥ 3 metabolic equivalents) will be identified and total daily energy expenditure will be computed to examine whether these variables influence stress levels or overeating episodes. Participants in the exercise condition will also be asked to wear this armband during all exercise sessions as these data will be used to confirm participants self-reported physical activity over the 12-week intervention period.

Fitness testing: A graded exercise test (GXT) to 75% of age-predicted maximal heart rate will be conducted at baseline and 12 weeks. Participants will walk on a treadmill at 3.0 mph and the incline of the treadmill will increase every two minutes until the subject's HR reaches 75% of their age-predicted maximum. Time on the treadmill and the estimated MET value upon test completion will be used to assess changes in fitness over time.

Food choice decision-making computer task: Participants will complete the food choice decision making task as part of their 12-week assessment visit. Using the methods employed in Hare and colleagues (2009) each participant will provide health and taste ratings on 150 different food items using a 5-pt scale¹. Foods include a range of unhealthy (e.g., chips or candy bars) and healthier (e.g., apples or broccoli) items. From these ratings a food rated as neutral in both taste and health will be selected for each individual participant as a reference item for the decision-making portion of the task. Participants then decide for each of the other food items if they would rather eat that target food or the reference item using a 4-pt scale (strong yes, yes, no, strong no) to note the strength of each choice. Special emphasis will be placed on these decisions by informing participants that one trial will be randomly selected and they must eat the food that they chose at the end of the experiment. In this way participants are encouraged to make honest, true-to-life judgments as any one trial could be the one selected. Ratings and decision data will allow us to determine the degree to which participants value health and taste in their decision-making (i.e., the extent to which ratings of food health and tastiness independently correspond to choices).

Questionnaires to be administered at baseline and 12 weeks:

- Three-Factor Eating Questionnaire (TFEQ)

- Eating Self Efficacy Scale (ESES)
- Perceived Stress Scale (PSS)
- Weight Bias Internalization Scale (WBIS)
- Distress Tolerance Scale (DTS)
- Pain Catastrophizing Scale (PCS)
- Barratt Impulsiveness Scale (BIS)
- Modified Trait Food-Cravings Questionnaire (FCQ-T)
- Power of food scale (PFS)
- Bull's Eye II
- Self-regulation Questionnaire for Exercise (SRQ-E)
- Food craving Inventory (FCI)
- Paffenbarger Physical Activity Questionnaire (PPAQ)

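### Does the primary comparison suffer because the follow-up smartphone monitoring window is not given in study days?

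*Protocol*

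**What the plan says.** The SAP's Primary Aim compares the arms on stress-induced overeating, taken from smartphone surveys, at 12 weeks. Its time term is a day indicator tied to the monitoring period and is not anchored to a study day.

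The protocol's timing statements are these:

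- **Study overview:** prompts five times a day for 14 days, at baseline and at 12 weeks. Payment for answered prompts is introduced with "At week 12, participants will receive".
- **EMA protocol:** "Participants will be asked to carry their smartphone for 14 days at baseline and 14 days at the end of the intervention".
- **In-person visit:** one sentence covers both the baseline and the 12-week visit. Participants receive an armband and "will be instructed on how to respond to the EMA prompts over the 14-day EMA period".
- **Exercise condition:** "During Weeks 5-12, participants will engage in 1 supervised visit/week". Exercise participants hold an armband throughout: "participants will be given an armband to wear over the 12-week period during all exercise sessions".
- **Delayed exercise condition:** participants "will be asked not to change their exercise or eating habits over the 12-week period". Then, "following the completion of the 12-week assessment period, participants will be given two options". Those who choose the full programme are assessed again at 24 weeks.

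**The concern.** A 14-day measurement cannot take place at a single time point, so a nominal 12-week label leaves open whether the window ends at week 12 or starts there. The visit logistics suggest one answer and other details suggest another. At baseline, equipping and instruction clearly come before monitoring. If the 12-week visit works the same way and falls at the end of the programme, the second window runs afterwards. Payment at week 12 and the 24-week assessment of the delayed arm fit a window that has closed by week 12.

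The distinction could matter. Supervised sessions, exercise payments and the delayed arm's request not to change habits are described only for the 12 weeks. If exercise fell once those supports stopped, a later window would weaken the contrast. The primary result would then describe overeating after the programme rather than during it, and a reader could not tell which.

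**Working it through.** The plan states no figure for this window, so there is none to reproduce. The check is a day count and a comparison of passages.

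**Inputs.** From the protocol: a 12-week programme (12 × 7 = 84 days, days 1-84), a 14-day window, 5 prompts a day, exercise pay of $10 a week plus a $50 bonus, and a 24-week reassessment. Assumed here: the visit falls on day V and monitoring starts the next day. The values of V below are illustrative.

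**Days on programme.** The window is V+1 to V+14, and days on programme = min(14, max(0, 84 − V)).

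| Visit day V | Window | Days on programme | Prompts on programme (× 5) |
|---|---|---|---|
| 70 | 71-84 | 14 of 14 | 70 of 70 |
| 77 | 78-91 | 7 of 14 | 35 of 70 |
| 84 | 85-98 | 0 of 14 | 0 of 70 |

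The maximum number of prompts is 5 × 14 = 70 in every row. The choice changes the exposure being measured, not the amount of data.

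**Exercise pay.** 12 × $10 + $50 = $170, which is the protocol's stated total. Nothing remains to be paid for weeks 13-14.

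**Delayed arm.** A window ending on day 84 lets the 84-day programme run on days 85-168, and 168 / 7 = 24 weeks, as stated. A window on days 85-98 moves the programme to days 99-182, and 182 / 7 = 26 weeks. This favours the earlier window, but only if 24 weeks is meant as an exact date and not as a label for the assessment round.

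**How firm is the conflict?** The explicit timing statements are 12 weeks (Study overview, SAP) and the end of the intervention (EMA protocol). Neither places the window after the programme. That reading rests on the single visit sentence. The sentence suits baseline, when monitoring is new; by 12 weeks every participant has already done 14 days of it, and the exercise arm already has an armband. On the other side, the payment sentence may only mean that the 12-week round is the paid one, since baseline is not. Read that way, the passages are imprecise but do not contradict each other.

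**Does the window affect validity?** Three features of the protocol protect the comparison under either reading:

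1. The delayed arm completes the same assessments as the exercise arm, so a common window adds no systematic difference between arms.
2. The delayed arm is offered exercise only after its 12-week assessment period, and the protocol treats the prompts as part of that assessment. Overlap with the delayed programme is therefore excluded.
3. Armband wear coincides with the prompts, so activity in the window is recorded whichever days were used.

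The SAP's model needs no study-day anchor and is unchanged under either reading.

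**The case for a change.** The strongest case for a change is that the In-person visit section describes one 12-week visit that both measures weight and starts the monitoring. On that wording, a visit at week 12 puts the window in weeks 13-14, while a visit on day 70 that lets the window close by day 84 measures the 12-week weight at week 10. One visit cannot do both, and no separate hand-over is described. The two windows also answer different questions: overeating during supervised, paid exercise, or after those supports have ended. One sentence in study days would settle it.

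Part of this stands. The window is not written down, and the wording alone does not fix it. But the argument shows a choice of what to estimate, not an error. Nothing in the documents requires an on-programme effect, and insisting on days 71-84 would need either an earlier weight measurement or an added hand-over. Most exercise in weeks 5-12 may already be unsupervised, so a sharp change at day 84 cannot be assumed. The SAP, dated 9.11.19, describes the analysis in the past tense, so new scheduling text would probably change nothing that was done.

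**Conclusion.** No change to the plan is needed. The study days of the follow-up monitoring are a missing detail. The most natural reading is about weeks 11-12, and the later reading is possible but rests on one logistics sentence. The two windows share 0 of 14 days, yet either supports a valid randomised comparison with up to 70 prompts per participant. No bias, wrong figure or power loss has been shown, and the size of any dilution cannot be derived from the documents.

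This rests on two assumptions: that both arms were monitored on the same schedule, as the protocol's common assessments imply, and that prompt times were kept, which is likely because prompts went out by text with a 45-minute response limit. An analyst can then give the actual dates by arm, relative to programme end, alongside the armband activity. That clarifies the description of the effect without altering the design or the analysis.

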Exercise as a buffer against stress induced overeating
ClinicalTrials.gov #: NCT02936076

Statistical Analysis Plan
9.11.19

Primary Aim: To compare exercise and delayed exercise conditions on stress-induced overeating (measured via smartphone surveys) at 12 weeks.

Analysis plan: Effects of exercise vs. delayed exercise on stress-induced overeating was examined using a longitudinal regression model implemented with Generalized Estimating Equations (GEE's) with robust standard errors. GEE's using a logit link and further adjusted error terms for the clustered nature of the data. Models included specifications of time (a time-varying indicator of day, indexed by monitoring period).

Secondary Aim 1: To compare exercise and delayed exercise conditions on changes in body weight from baseline to 12 weeks.

Analysis plan: Percent weight loss from baseline to 12 weeks was calculated for each participant and independent samples t-test were used to examine whether exercise and delayed exercise conditions differed from one another.

Secondary Aim 2: To compare exercise and delayed exercise conditions on their self-reported perceived stress at 12 weeks.

Analysis plan: A univariate ANOVA, controlling for baseline stress levels was used to assess whether exercise and delayed exercise conditions differed from one another at 12 weeks.

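### The primary GEE test names plain robust standard errors; a bias-corrected sandwich with a t reference would keep its type I error nearer nominal if few women are analysed

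*SAP*

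**What the plan says.** In the SAP, the analysis plan under Primary Aim specifies a longitudinal regression "implemented with Generalized Estimating Equations (GEE's) with robust standard errors". It adds a logit link, says the models "further adjusted error terms for the clustered nature of the data", and includes a day term defined within each monitoring period. It names no finite-sample variance correction, degrees of freedom, z or t reference, or significance level.

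Under Secondary Aim 1, the SAP compares percent weight loss by a method whose reference distribution does depend on the number of women: "independent samples t-test were used to examine whether exercise and delayed exercise conditions differed from one another".

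The Protocol's study overview sets the unit of allocation: "Participants will then be randomized to a 12-week exercise training program or a delayed exercise condition". Its EMA section sets the measurement schedule: "All entries will be made in response to 5 semi-random prompts delivered throughout the day", for 14 days at baseline and 14 days at the end of the intervention. The text available for this review, from which title and consent pages had been removed, states no number of women, allocation ratio or power calculation.

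**The concern.** Each woman has one condition, so the women are the independent units for the primary comparison. Up to 5 × 14 = 70 prompts per period make each woman's own rate more precise. They do not increase the number of units on which the between-condition variance is estimated, and several thousand prompt records can hide this.

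A clustering adjustment handles correlation among one woman's prompts. It does not by itself deal with two known features of the ordinary sandwich when clusters are few: the variance estimate is biased downwards, and it is itself variable, which a z reference ignores. Both push towards rejecting too often and towards intervals that cover too little. On a primary test, a borderline p-value could turn on this choice.

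**Working it through.** **Inputs from the documents.** Allocation per woman; 5 prompts a day for 14 days per period; and a baseline response floor, since women under 80% "compliance to the EMA monitoring at baseline or those with poor compliance to wearing the armband will not be eligible to participate". That floor is 0.80 × 70 = 56 prompts.

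**Assumed inputs.** Two-sided 5% level, number of women N from 20 to 200, and 1:1 allocation. The simulations also assume the event rate, between-woman spread, response share, share of stressed prompts and an independence working matrix. The plan gives no sample size or error rate to reproduce.

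**Closed form.** Compare the means of n = N/2 women per arm, treated as normal with equal variance. The uncorrected sandwich divides the sum of squares by n instead of n − 1, so the z test rejects when |T| > 1.96 × √((n − 1)/n), where T follows t on N − 2 degrees of freedom. The interval with an unbiased variance and a t reference is wider by the factor t(0.975, N − 2)/1.96 × √(n/(n − 1)).

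| N | n | df | 1.96 × √((n − 1)/n) | Type I error | t(0.975, df) | Width factor |
|---|---|---|---|---|---|---|
| 20 | 10 | 18 | 1.859 | 7.9% | 2.101 | 1.13 |
| 40 | 20 | 38 | 1.910 | 6.4% | 2.024 | 1.06 |
| 60 | 30 | 58 | 1.927 | 5.9% | 2.002 | 1.04 |
| 100 | 50 | 98 | 1.940 | 5.5% | 1.984 | 1.02 |
| 200 | 100 | 198 | 1.950 | 5.3% | 1.972 | 1.01 |

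A t reference without the variance correction still gives 6.2% at N = 20 and 5.4% at 60, so both parts are needed. With 2:1 allocation (from normal draws) the z test gives 8.8% at N = 21, 6.2% at 60 and 5.4% at 201.

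**Simulated logit GEE, uncorrected sandwich with z, no true effect.** Each range covers 12-week-only and condition-by-period models, using all prompts or stressed prompts only (5000 replicates per cell, Monte Carlo error about 0.3 to 0.5 points).

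| Assumed event rate | N = 20 | 40 | 60 | 100 | 200 |
|---|---|---|---|---|---|
| 20% | 8.3–9.4% | 6.7–7.0% | 6.1–6.3% | 5.4–6.4% | 5.1–5.3% |
| 10% | 9.4–11.0% | 7.2–7.7% | 6.5–7.3% | 5.7–6.3% | 5.3–5.8% |
| 5% | 10.3–12.3% | 7.7–9.4% | 6.7–8.3% | 6.6–7.3% | 5.4–6.3% |

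The 5% row is an unfavourable case. It is less likely here because the Protocol excludes "those who do not endorse stress-eating".

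A second simulation, with event rates of 10% to 20% and some scenarios restricted to stressed prompts, gave 8.0–13.1% at N = 20, 6.5–9.1% at 40, 5.9–7.4% at 60 and 4.9–6.0% at 200.

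**After the correction.** Mancl-DeRouen with t on N − 2, over all N in the first simulation, gave 4.0–5.4% with 20% events, 4.7–5.9% with 10% and 5.0–7.5% with 5%. In the closed-form setting, unbiased variance plus t gives exactly 5%.

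**The case against.** The strongest reply is that no error in the plan has been shown. Harm requires that an uncorrected sandwich with z was used and that few women were analysed, and the documents establish neither. Software defaults differ, and the clustering sentence leaves open what was done. Over much of the range the effect is small: at 20% events the simulated excess is 0.1 to 0.3 points at 200 women. The proposed estimator is one of several, and it does not guarantee 5% when events are rare.

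Most of this stands, and it rules out several stronger readings. A reader might infer that the reported primary result has an inflated error rate; the documents do not support that, because the reference distribution and the number of women are both unknown. A reader might infer that the prompts were analysed as if independent; the SAP says the opposite. A reader might also infer that the number of women alone fixes the excess. It does not: at N = 20 the first simulation runs from 8.3% to 12.3% depending on event rate, prompt set and model. Finally, the absence of a stated N, correction or reference is only missing detail and would not carry the point by itself.

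What survives is that a concrete alternative to plain robust errors brings the test closer to nominal, using data already collected. If many women were analysed the correction changes almost nothing; if few were, it matters.

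**Conclusion.** The point holds as an inexpensive improvement to the primary test. It is not a demonstrated error. Conditional on an uncorrected sandwich with z, and on an assumed two-sided 5% level and 1:1 allocation, the closed-form excess falls from about 2.9 points at 20 women (7.9 − 5.0) to 0.3 points at 200 (5.3 − 5.0). It is material at small N and minor by about 100 to 200 women, with no sharp cut-off. Rare events, unevenly spread stressed prompts or unequal allocation can make it larger. Where this trial lies on that range cannot be determined from the documents.

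**What to change.** Compute the primary test and confidence interval with a bias-corrected sandwich clustered on participant (Mancl-DeRouen or a comparable correction such as Kauermann-Carroll). Use a t reference on the number of women minus the number of between-participant parameters, which is N − 2 with intercept and condition only. Report the number of women analysed per condition. The SAP is written in the past tense; if the analysis is already done, give the corrected result alongside the one obtained and do not replace it.

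Optionally, add a permutation test of condition between women as a sensitivity check, respecting any blocking or stratification; the documents describe none. In a check with assumed blocks of 4, reshuffling within blocks gave 4.6–5.7%. Ignoring blocks under enrolment drift was conservative, at 2.8–4.4%.

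The cost is one or two SAP sentences, a few lines of code and a wider interval. Beyond the closed-form widening shown above, simulated Mancl-DeRouen intervals with t were 19–20% wider at 20 women, 9% at 40, 6% at 60, 3–4% at 100 and 2% at 200. If stressed prompts differ widely between women, the figure is up to 27% at 20 and 8% at 60. The correction reduces the excess but may leave a mild one if overeating is rare.

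### The SAP's primary GEE does not say which coefficient is the 12-week condition effect, and makes no stated use of baseline stress-induced overeating

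*SAP*

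**What the plan says.** The SAP states its primary aim as: "To compare exercise and delayed exercise conditions on stress-induced overeating (measured via smartphone surveys) at 12 weeks". The analysis plan continues: "Effects of exercise vs. delayed exercise on stress-induced overeating was examined using a longitudinal regression model", fitted by GEE with robust standard errors, "using a logit link and further adjusted error terms for the clustered nature of the data". The one model term it spells out is time: "Models included specifications of time (a time-varying indicator of day, indexed by monitoring period".

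The protocol's EMA section gives two monitoring periods before the primary comparison: "Participants will be asked to carry their smartphone for 14 days at baseline and 14 days at the end of the intervention". The optional 24-week assessment for the delayed arm comes later. Baseline EMA data should be nearly complete for everyone randomised, because the eligibility criteria exclude "individuals with <80% compliance to the EMA monitoring at baseline".

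Secondary Aim 2 in the same SAP does state an adjustment for the baseline value of its outcome. The primary aim states none.

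**The concern.** The aim needs one number, the difference between conditions at 12 weeks. The SAP does not say which coefficient supplies it. A condition term is clearly implied, but not how it relates to period. Naming the monitoring period in the time term suggests, without stating, that baseline prompts are in the outcome vector.

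Three consequences are possible:

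- **Both periods, main effects only.** The condition coefficient blends a pre-intervention difference, zero in expectation under randomisation, with the 12-week effect. It is pulled towards the null and is not the estimand in the aim.
- **12-week prompts only.** The contrast is right, but the baseline EMA is unused. Precision may be lost, and the estimate can drift if dropout is related to baseline overeating.
- **A suitable baseline-adjusted or two-period model.** The analysis is sound, but the reader cannot know that it was the one planned.

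**Working it through.** **Inputs.** From the protocol: 5 prompts a day for 14 days gives 5 × 14 = 70 prompts per period, and 80% compliance is 0.80 × 70 = 56. Neither document gives a sample size, event rate, effect size, correlation or dropout rate, so there is no planned figure to reproduce. Everything below is illustrative. Base assumptions: overeating at 20% of prompts, person-period logit SD 0.89, true population-averaged 12-week odds ratio 0.60, and baseline-to-12-week correlation 0.2, 0.4, 0.6 or 0.8.

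**Step 1: dilution under a pooled main effect.** Take 70 prompts in each period, independence working correlation and no change in the delayed arm.

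- Exercise arm at 12 weeks: odds 0.60 × 0.25 = 0.15, so the rate is 0.15/1.15 = 0.1304. The other three cells are 0.20.
- True log odds ratio: ln 0.60 = −0.511.
- A logit model with condition and period but no interaction must reproduce the margins. Each delayed-arm or baseline margin is 0.20 + 0.20 = 0.400. Each exercise-arm or 12-week margin is 0.20 + 0.1304 = 0.3304.
- The fitted rates are 0.2187 (delayed, baseline), 0.1813 (delayed, 12 weeks, and exercise, baseline) and 0.1491 (exercise, 12 weeks).
- Condition coefficient: logit(0.1813) − logit(0.2187) = −1.508 + 1.273 = about −0.234, an odds ratio of 0.79.
- Recovery: 0.234/0.511 = 0.46.

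Over event rates of 10% to 35%, odds ratios of 0.4 to 0.8 and baseline-to-12-week prompt counts from 63:32 to 56:70, recovery is 0.26 to 0.55. Adding a period shift of −0.3 to +0.3 logit widens this to 0.21 to 0.59 (median 0.43; 34 of 162 settings above 0.50). At a 20% rate, a true 0.60 then appears as 0.75 to 0.88. With a single prompt-level exchangeable correlation, recovery is 0.00 to 0.50, median 0.27. The working correlation moves the estimate here because the pooled mean model is wrong. If the target is a stress-by-condition term, pooling it over periods recovers 0.26 to 0.55.

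**Step 2: power at an assumed N of 50.** Logistic GEE, robust SE, 1.96 cut-off, 3000 replicates (Monte Carlo error about 0.9 points).

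| Model | corr. 0.2 | 0.4 | 0.6 | 0.8 |
|---|---|---|---|---|
| Pooled main effect | 23% | 22% | 19% | 18% |
| 12-week prompts only | 52% | 54% | 51% | 52% |
| (a) 12-week prompts, baseline rate as covariate | 53% | 57% | 62% | 77% |
| (b) two periods, arms equal at baseline, separate within- and between-period correlations | 54% | 58% | 63% | 78% |
| (b) with a single exchangeable correlation | 40% | 45% | 55% | 74% |

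Form (b) under independence equals the 12-week-only analysis. A repeat run of (a) gave 54%, 56%, 63% and 76%. With no true effect, rejection was 6.3% to 8.0% over all models, so all powers are slightly inflated.

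Reduction in mean robust SE against 12-week only: (a) 1%, 5%, 11%, 23%; (b) 3%, 7%, 15%, 28%. Measured by the empirical SD of the estimates: (a) 0%, 5%, 10%, 21%; (b) 1%, 7%, 13%, 26%. If only stressed prompts count (assumed 30%), the SE reduction is 0% to 11% for (a) and 3% to 16% for (b).

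**Step 3: dropout.** Suppose 25% drop out of the exercise arm, more often at higher baseline rates, and 10% drop out of the other arm at random. The 12-week-only odds ratio becomes 0.59, 0.57, 0.55 and 0.53 against a true 0.60. Form (a) stays within 0.005 of its no-dropout value, and (b) stays at 0.60 to 0.61.

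**The case against.** The strongest reply is that the dilution belongs to a model the SAP never describes. The aim names 12 weeks, the effect of condition is stated, and saying that models included time does not make time the only term. A pooled main effect is the reading least compatible with the aim. This stands as a limit: the omission is certain, the harm conditional. But the text does not exclude that model, and an implied condition main effect in a two-period fit is exactly the diluted coefficient.

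Other points stand in part:

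- With robust SEs and a correct mean model, the working correlation mainly affects efficiency. It is the least serious of the omissions.
- The lowest recoveries need far fewer prompts at 12 weeks than at baseline. The protocol pays at week 12 "for each EMA prompt responded to within 45 minutes", so the counts may be equal or tilt the other way. With equal prompts and no period shift, recovery is 0.41 to 0.49.
- The dropout pattern is invented; at correlation 0.2 its effect is small.
- The two-correlation version of (b) was not cross-checked against a standard package.

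An ordinary unconstrained condition-by-period GEE is arguably the most natural reading. Under the N = 50 assumptions its power is 37%, 43%, 53% to 55% and 71% to 73% over the four correlations: below (a) throughout, and below 12-week only at the two lowest. It beats 12-week only when the correlation is high.

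Finally, the SAP is in the past tense, so a new primary model would be post hoc. That calls for labelling the change, not for leaving the test undefined.

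**Conclusion.** The concern holds and should be fixed. The SAP does not fix which odds ratio answers the primary aim, and neither document fills the gap. That conclusion needs no assumptions.

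The size does. A pooled two-period main effect would recover about half or less of the 12-week log odds ratio in most settings tried, and never more than 0.59. At N = 50 it would cut power from about 52% to about 20%. A 12-week-only test is not biased by pooling. What it gives up ranges from almost nothing at low between-period correlation to about 25 points of power at correlation 0.8, plus protection against dropout related to baseline overeating. The event rate, odds ratio, variance, correlation, N and dropout pattern are all assumed. No claim is made that the fitted analysis was wrong.

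**What to change.** State which monitoring periods entered the model, and make the 12-week condition effect the primary test, using the baseline EMA outcome in one of two ways:

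- **(a)** a logit GEE with robust SEs on the 12-week prompts, with each participant's baseline rate of the same outcome (for example its empirical logit) as a covariate; or
- **(b)** a two-period logit GEE with the arms constrained equal at baseline and the condition-by-period term as the test. Name a working correlation that lets the between-period correlation differ from the within-period one. Independence gains nothing from baseline here, and a single exchangeable correlation can do worse than ignoring baseline.

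Either is acceptable, and their power is practically the same. Keep day as the time term. Define how the stress and overeating items combine into the outcome, identically in both periods. If the target is a stress-by-condition term, test its 12-week value. Do not report a pooled two-period condition main effect as the 12-week effect.

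The cost is one or two sentences of SAP text and a re-fit, with no new data; (b) may take more programming. Under (a) the odds ratio is conditional on the baseline rate (about 0.58 to 0.59 against 0.60 in the N = 50 runs); under (b) it stays population-averaged. If the analysis has already been run, report the as-fitted result beside the adjusted one and label the change.
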